We are proposing the following changes: 1) We are allowing clinician rated measures to be completed by phone for all visits when needed/indicated to reduce subject burden and protocol deviations. Subsequently, we have added a protocol for patients expressing active suicidal ideation over the phone. 2) We are updating the protocol to allow for the initial screening physical exam and EKG to be conducted at the baseline visit to accommodate clinician availability. 3) When blood cannot be obtained during the study visit by a member of the research staff, we are allowing the blood to be drawn at the phlebotomy lab at the MGH main hospital to accommodate the subject's schedule. 4) The psychoeducational session that takes place during the initial baseline (visit 2) and the repeat baseline (DYG, Visit 7) can now take place over the phone with [name] to accommodate patient's schedules. 5) We are allowing participants to bring back their sleep diaries and saliva samples at the following visit if they forget them, as long as they were collected during the appropriate time. 6) We are adding the option to be re-contacted for future research studies to the informed consent. 7) The yoga studios have changed names and owners.

Version Number: 1.4

Version Date: July 10, 2017

Summary of Revisions Made:

We are proposing the following changes: 1) We are increasing the amount of blood collected throughout the study from a total of 13ml to 30ml per visit, resulting in a total amount of blood collected of 131mL for the immediate yoga group, and 221mL for the delayed yoga group. 2) We have added the University of Rhode Island Change Assessment Scale (URICA), which assess for readiness to change, to the baseline and end-of-study visits. 3) We are modifying our inclusion/exclusion criteria to specify that the consumption of coffee or other caffeinated beverages is allowable, and to alter the length required for a participant to be on a stable psychiatric medication prior to enrolling to the study from <3 months to <2 months, with a stable dose for <4 weeks. 4) We would like to ask participants to complete two paper-copy surveys (the EIFI and the STAI-State) 30 minutes pre and post each yoga class they attend. The questionnaires will be handed to participants after they are randomized at the end of their Baseline visit. 5) We included a column on the C-SSRS conducted at screen to assess for symptoms in the “past year”, in addition to “lifetime”. 6) We created an “informational form” to hand out to participants at baseline, which contains information about the studio locations and class scheduled, as well as reminders of how many classes to attend, which classes to attend, and that participants can attend classes at both studios for free for the duration of the study. 7) We updated the study protocol to specify how our randomization procedures are conducted (i.e., that participants are randomized at the end of their baseline visits by a research coordinator, and only informed of their group assignment once they have completed all study-measures). 8) We have changed the frequency of [name] check-in calls with participants to once every two weeks, on weeks when participants do not come in to the program for an in-person assessment visit.

STUDY TEAM ROSTER

Principal Investigator: [name]
[name]
[name]
[contact]
[contact]
Email: [contact]

Primary Mentor: [name]
[name]
[name]
[name]
[contact]
[contact]
Email: [contact]

Co-Mentor: [name], PhD
[name]
[name]
[contact]
[contact]
Email: [contact]

Co-Mentor: [name]
[name]
[name]
[contact]
[contact]
Email: [contact]

Medical Monitor: [name], MPH
[name]

1. STUDY OBJECTIVES

1.1 Primary Objective

Primary Aim I: To recruit and retain adults with depressive symptoms into a controlled trial of hyperthermic yoga, randomizing 40 participants to each the immediate yoga group (IYG) and delayed yoga group (DYG; control group) with seventy-five percent retention in both groups.

Hypothesis 1a: Seventy-five percent of the each group will complete a week-8 assessment.

Hypothesis 1b: Acceptability of hyperthermic yoga will be high on the Acceptability Interview.

Primary Aim II: To collect the Inventory of Depressive Symptomatology – Clinician Rated (IDS-CR) scores at screening; baseline; and weeks-1, -3, -5 and -8 to evaluate the efficacy of hyperthermic yoga for depressive symptoms.

Hypothesis II: The IYG will have greater decreases in Inventory of Depressive Symptomatology – Clinician Rated (IDS-CR) scores after 8-weeks compared to the DYG.

Primary Aim III: To collect (a) physiological and (b) psychological mediators of hyperthermic yoga in the IYG and DYG group at screening; baseline; weeks-1, -3, -5 and -8 to evaluate treatment response in the IYG compared to the DYG.

Hypothesis IIIa: Salivary cortisol, and inflammatory markers (i.e., Tumor Necrosis Factor [TNF- α], Interleukin-6 [IL-6], and C-Reactive Protein [CRP]) will significantly decrease following 5- and 8-weeks of hyperthermic yoga in the IYG compared to the DYG.

Hypothesis IIIb: Perceived stress, mindfulness, and rumination will improve by 5- and 8-weeks in the IYG compared to the DYG.

1.2 Secondary Objectives

Secondary Aim I: To collect measures of quality of life, general health, physical functioning, decreased perceived stress, anxiety, and sleep in the IYG and DYG at screening; baseline; and weeks-1, -3, -5 and -8 to evaluate hyperthermic yoga for secondary outcome measures.

Secondary Hypothesis I: The IYG will have significant improvements in quality of life, general health, physical functioning, perceived stress, anxiety, and sleep compared to the DYG.

Secondary Aim II (exploratory): To evaluate the long-term effects of the yoga intervention (1-month post intervention), while controlling for continued yoga participation.

Secondary Hypothesis II: Subjects who choose to continue the yoga practice, either in the IYG or DYG, will have increased effects at 1-month post intervention, per the primary and secondary outcome measures compared to the week-8 assessment.

2. BACKGROUND AND RATIONALE

2.1 Background on Condition, Disease, or Other Primary Study Focus

Depression is associated with significant mortality, morbidity, and disability, and is the fourth leading cause of global disease burden¹. By 2020, Major Depressive Disorder (MDD) is projected to be the second leading cause of global disability in developed nations². Even though more people are receiving treatments for depression, there is no evidence that the associated morbidity and mortality have significantly decreased. The Sequenced Treatment Alternatives to Relieve Depression (STAR*D) Study suggested relatively “weak effects” of antidepressants³. In addition, antidepressants also have common side effects, such as weight gain, sexual dysfunction, fatigue, and others⁴. Electroconvulsive therapy, and more recently ketamine infusion, provide more immediate relief to those with severe depression³, though these benefits are often short-lived. Cognitive Behavioral Therapy (CBT), although effective, demonstrates remission rates no better than antidepressants^{5,6}. The modest effects of current treatments may be due to their inability to fully address the physiological dysregulation of the stress response system⁷.

2.2 Study Rationale

Proposed Intervention: Bikram Yoga (BY) is a standardized type of hyperthermic yoga, which synergistically combines Hatha Yoga postures, intensive exercise, mindfulness, and thermal therapy. It consists of 26 sequenced postures and two breathing exercises, practiced for 90 minutes in a room heated to 105-110°F with 40–60% relative humidity. Table 1 summarizes the hypothesized active elements of BY.

Table 1. Mechanisms of Bikram Yoga.

Mechanism and Evidence Base	Inclusion in Bikram Yoga Protocol
Yoga: Yoga demonstrates antidepressant effects ⁸⁻¹² .	Includes postures indicated for depression, i.e., backbends and inversions ⁸ .
Intensive Exercise: Exercise demonstrates antidepressant effects ¹³ , and more intensive exercise produces higher remission rates as an augmentation for resistant MDD ¹⁴ .	BY presents a more intensive form of exercise than most yoga modalities, and produces high metabolic energy output ¹⁵ .
Mindfulness: Mindfulness-based interventions reduce depressive symptoms and prevent relapse ¹⁶ .	The practice discharges agitation and facilitates mindfulness. Mastery of uncomfortable sensations may generalize to maintaining a calm mind during times of high stress.
Thermal Therapy: Heat ¹⁷⁻¹⁹ , thermal therapy ²⁰⁻²³ and fever ²⁴ demonstrate antidepressant potential.	The heat (105-110°F) may enhance the benefits of the standard Hatha Yoga postures and allow for greater stretching of muscles ²⁵ , in addition to providing anxiolytic effects ²⁶ .

Characteristics of Bikram Yoga for Clinical Trials: Table 2 outlines the features that differentiate Bikram Yoga from other forms of yoga, and highlights the suitability of its use in clinical trials for depression.

Table 2. Features of Bikram Yoga.

Bikram Yoga Features	Clinical Trial Applicability
Classes are standardized in time, dialogue, posture sequence/duration, and room conditions. The unified consistent protocol allows for a rigorous clinical trial design because all patients assigned to yoga get the same intervention.	The lack of standardized yoga protocols ²⁷ hinders methodological rigor in the yoga for depression literature base ⁹ .
The standardized Bikram Yoga dialogue was designed to allow inexperienced students to safely complete the yoga postures ²⁵ .	The practice was developed so that participants of all levels would be able to take the classes ²⁵ .
Bikram Yoga focuses almost exclusively on the physicality of the practice, rather than the spiritual components of yoga.	Yoga modalities range in degree of physical and/or spiritual emphasis ²⁷ . The physical focus may have broader, secular-based appeal to US public.
Widely Available: 285 Bikram Yoga studios in the US and 217 Bikram Yoga studios abroad, covering 42 countries and 464 cities; 18 Bikram Yoga studios in Massachusetts.	The intervention has broad potential for quick dissemination.

Yoga as a Treatment for Depression: Evidence is accumulating to support yoga as a treatment for depression. A 2005 literature review found 5 randomized controlled trials (RCTs)¹¹, whereas a 2013 meta-analysis found 12 RCTs¹². Reviews suggest that yoga is a promising treatment for depression, but consistently note that a lack of rigorous study methodology prevents the firm conclusion that yoga be considered a treatment for depression^{9, 12, 28}. Methodological limitations include: heterogeneity of yoga interventions and patient samples; inadequate sample size and randomization procedures; lack of intention-to-treat analysis and blinding of outcome assessors; inadequate control groups; and unreported dropout, relapse, and remission rates^{9, 12}. Despite these flaws, the 2013 meta-analysis¹² did find moderate evidence for the short-term effects of yoga compared to usual care. A 2013 systematic review of yoga for depression¹⁰ affirmed “Grade B” evidence for yoga as an acute treatment for depression. One controlled study used an Iyengar yoga treatment, a form of hatha yoga, that included back bends, inversions and vigorous standing postures thought to be particularly effective for alleviating depression⁸. These postures are also used in Bikram Yoga, which is also a form of hatha yoga. The Beck Depression Inventory (BDI) and Spielberger State-Trait Anxiety Index (STAI) measured mood and anxiety. Subjects had baseline BDI scores of 10 to 15 (mild-to-moderate depressive symptoms), similar to the proposed study. The 5-week yoga intervention decreased depression and anxiety, using similar measures to the proposed study. The evidence has been promising enough to warrant two current rigorous NIH R01 funded RCTs for non-heated yoga (NIH RePORTER: 1) PI: [name] [NCCAM], and 2) PI: Uebelacker [NINR]). The proposed study has been constructed to address the concerns and apply rigorous methodology to an unexplored form of yoga.

Bikram Yoga Research: While there is no literature on Bikram Yoga for depression, several studies of Bikram Yoga demonstrate improvements in physiological and psychological processes implicated in depression. **Physiologically:** In a recent 8-week pilot trial, 3 weekly

Bikram Yoga classes improved glucose tolerance in 15 older obese adults compared to 14 young lean subjects. This supports Bikram Yoga as a therapeutic tool for metabolic dysfunction²⁹, and depression is associated with metabolic disorders³⁰. Another study found that 8 weeks of 3 weekly Bikram Yoga classes improved arterial stiffness in 24 younger adults (30±1 years), and significantly reduced insulin resistance in 18 older adults (53±2 years)³¹. The relationship between depressive and anxiety disorders and early markers of arterial stiffness³², indicates a common pathophysiology with depression. **Psychologically:** In an uncontrolled study of 54 healthy individuals, Bikram Yoga improved mindfulness and decreased stress³³, suggesting benefits in depression via effects on mindfulness and perceived stress. In an unpublished dissertation, DeBoer et al.³⁴ reported preliminary completer data of twice weekly Bikram Yoga classes (n=27) versus a waitlist control (n=25) for women (ages 25-45) with stress-induced eating and high perceived stress. This study demonstrated a dropout rate of 11.5%, lower than in most depression trials. The 4 subjects who discontinued yoga did so in the initial stages of the practice. This study provided preliminary evidence of the acceptability of recruiting and retaining a psychiatric population for this intervention. The effect size for the change in the Beck Depression Inventory (BDI-II)³⁵, based on Cohen's *d*, was medium (0.54), suggesting an advantage for Bikram Yoga over the waitlist. As this study did not require depressive symptoms for entry, the effect size for depression in the proposed study will likely be higher. The Beck Anxiety Inventory (BAI)³⁶ demonstrated a large effect for Bikram Yoga over control (*d*=1.19). There were also large effects for Bikram Yoga's ability to reduce scores on the Ruminative Responses Scale (RRS)³⁷ (.76), the Perceived Stress Scale (PSS)³⁸ (.83), and the Response to Positive Affect Scale³⁹ (.76). I will include the PSS and RRS in our study as secondary outcome measures, due to these results.

Thermal Therapy for Depression: Whole-body hyperthermia is receiving attention as an antidepressant. A large effect size (*d*=1.13) was found 5-days post a single total-body hyperthermia session (mean time 126.7 minutes) in 16 medically healthy adults with MDD on the Centers for Epidemiological Studies Depression Scale (CES-D). Only 3 of the 16 subjects were on antidepressants (SSRIs). When the 13 SSRI-free subjects were analyzed separately, the effect sizes increased (*d*=1.4). These findings are consistent with studies of mood induced hyperthermia in medically ill populations^{23, 40}. In another study, fever induction in medication-free patients with melancholic MDD produced improvements in mood for all patients the day after induction, perhaps via inflammatory cytokines suppressing REM sleep, thus improving mood²⁴. In another study, 28 medication-free patients with mild depression and somatic complaints randomized to 4 weeks of 5x/week (20 sessions) thermal therapy vs. non-thermal therapy (60°C for 15 minutes followed by 30 minutes of bed rest with blanket) demonstrated improvement in somatic and mental complaints, hunger, and relaxation²¹. Other preliminary data also support heat's beneficial effect on mood^{17-19, 22}. Recent data suggest that Bikram Yoga similarly raises core body temperature¹⁵. There is evidence for a relationship between thermal regulation and serotonergic neural circuits controlling cognitive function and mood⁴¹. Depressed patients have disruption in thermoregulatory cooling, implicated in the maintenance of the disease⁴². Bikram Yoga offers both a mechanism for understanding this interaction and a means of treatment.

Yoga's Effects on the Stress Response Systems: Depression is linked to the body's physiological reaction to stress⁴³. Yoga may restore homeostasis by increasing

parasympathetic nervous system (PNS) activity, restoring gamma-amino-butyric acid (GABA) activity, and reducing physiological effects of stress⁷. This may occur through a variety of mechanisms, including stimulation of the vagus nerve⁷, related to vagus nerve stimulation for depression. **Hypothalamic-Pituitary-Adrenal Axis (HPA)**: depression is commonly associated with increased cortisol levels⁴³. Across populations yoga consistently reduces cortisol levels⁴⁷⁻⁵⁵. **Immune System Markers/Inflammatory Markers**: Inflammatory processes have been consistently implicated in the pathophysiology of depression⁵⁶. In a meta-analysis of dozens of studies, medically-healthy MDD patients exhibit elevated serum interleukin (IL)-6, IL-1 (esp. IL-1-beta), and acute phase C reactive protein (CRP)⁵⁷. Other studies report increased serum tumor necrosis factor alpha (TNF- α) in MDD patients^{56, 58}. Expert hatha yoga practitioners, compared to novices, had lower levels of inflammatory markers at baseline, during, and after a protocol of stress induction and subsequent participation in hatha yoga⁵⁹. In a non-randomized sample of patients with chronic diseases, inflammatory markers decreased after just ten days of yoga practice⁶⁰. These data support our rationale for measuring HPA (cortisol), and immune system function (inflammatory markers) in our sample before, during, and after treatment.

Yoga and Functional Measures: Yoga may improve quality of life and functional measures associated with MDD. **Quality of Life**: Yoga has demonstrated improvements in quality of life in medically ill populations⁶¹⁻⁶⁶. Since depression has a strong relationship with decreased quality of life⁶⁷, yoga may be of significant benefit. **Physical Functioning**: Depressed people have impairments in physical functioning similar to common chronic physical conditions⁶⁸⁻⁷⁰. Additionally, those with MDD and chronic illnesses have greater risk of subsequent illness, disability, and premature mortality⁷¹. In a meta-analysis of older adults, yoga may hold greater benefits than conventional exercise for health status, aerobic fitness, and strength⁷². In a recent literature review, yoga helped improve multiple markers of physical health⁷³.

Yoga and Secondary Outcomes: Anxiety: Symptoms of anxiety are often 40-50% comorbid with MDD⁷⁴⁻⁷⁶. Yoga may treat anxiety, though similar to the depression and yoga literature base, studies are methodologically flawed⁷⁷. **Sleep**: Sleep disturbance and depression have been linked to fragmentation of sleep architecture and likely share common biological pathways⁷⁸. Experienced Bikram Yoga practitioners using transition analysis had a faster return to sleep after nocturnal awakenings on nights when yoga was practiced that day compared to non-yoga days⁷⁹. Bikram Yoga may directly and/or indirectly improve mood by simultaneously improving sleep. Improved sleep regulation, via improved sleep efficiency and quality, may be a mechanism for yoga's antidepressant effects⁹.

3. STUDY DESIGN

The project is an acceptability, feasibility, and pilot efficacy trial of hyperthermic yoga vs. a waitlist control for 80 adults with at least mild depressive symptoms. The target enrollment for the study will be 160 to properly screen the number of needed randomized participants. The hyperthermic yoga intervention will take place in two community Bikram Yoga studios in the Boston area. Bikram Yoga Boston is owned by [name] and Bikram Yoga Cambridge is owned by [name]. Participants will attend classes at either of these studios, free of charge – i.e., the intervention will be community-delivered. Participants will be asked to attend

at least two weekly 90-minute Bikram Yoga classes during the 8-week intervention phase of the study. All research related assessments will take place at the Depression Clinical and Research Program (DCRP) at the Massachusetts General Hospital (MGH). The enrollment period for participants will depend upon the arm to which they are randomized: 1) immediate yoga group (IYG) will complete the protocol in approximately 15 weeks; and 2) the control or delayed yoga group (DYG) will complete the protocol in approximately 24 weeks.

Retention Strategies: Patients with depressive symptoms frequently have impaired motivation. In the only known RCT of hyperthermic yoga for a psychiatric population, subjects who dropped out tended to do so after 1-2 sessions. Most who got through this critical period completed the study³⁴. To address this: 1) study staff, the PI or designee, will administer a 50-minute pre-yoga baseline psychoeducation session with a preparatory handout, which they take home with them. 2) Participants will receive a bi-weekly telephone call from the PI, and when not available, another study staff member.

Subject Remuneration: Subjects in the DYG will be compensated for their time during the waitlist period (\$25 for baseline; week 1, 3, 5 and 8; total=\$125) to encourage participation. Subjects in IYG will only be paid for the 1-month follow up visit (\$25), as they will receive free yoga classes at the outset of the study. All subjects will receive \$30 per cortisol assessment.

4. SELECTION AND ENROLLMENT OF PARTICIPANTS

Inclusion Criteria

1. Adults ages 18-60
2. English language proficiency
3. Ability to provide informed consent
4. Score of >23 on the Inventory of Depressive Symptomatology – Clinician Rated (IDS-CR)⁸⁰
5. Able and willing to attend two 90-minute hyperthermic yoga sessions per week
6. Willingness to keep existing exercise regimen (even if that is sedentary) stable over study course
7. Women of childbearing potential must use an acceptable form of birth control
8. Membership to the Bikram Yoga Boston and Bikram Yoga Cambridge studios via studio websites
9. Willingness to adhere to hydration requirements (i.e., an additional four 8 oz servings of water pre- and post-yoga classes)

4.2 Exclusion Criteria

1. Pregnancy or planned pregnancy during study
2. History of psychiatric hospitalization within the past year
3. Active suicidal intent within the past year (“yes” on item 4 or 5 on the Columbia-Suicide Severity Rating Scale⁸¹)
4. History of neurologic disorders that could interfere in study participation
5. History of bipolar disorder, psychotic disorders, eating disorders, and/or substance abuse or dependence (within the last year), as per the Mini-International Neuropsychiatric Interview (MINI)⁸²
6. Psychotropic medication use that has been stable for <2 months, and at a stable dose for <4 weeks
7. Use of stimulant medications or diet pills during the study, or any pre-workout powders or liquids designed to provide excessive energy (excluding coffee or caffeinated beverages)
8. Positive urine toxicology screen due to illicit drug use or other exclusionary medications. (Potential false positives will be addressed on a case-by-case basis at the discretion of the investigator)
9. Active conditions which may also cause depressive symptoms (e.g. epilepsy, hypothyroidism)
10. Medical conditions that may make participation unsafe (e.g., diabetes [I & II], cardiovascular disease, hypertension [>140 systolic and/or >90 diastolic], hypotension [<90 systolic and/or <60 diastolic, during screening], orthostatic hypotension [systolic drop of 20 points or 10 point diastolic or heart rate increase by 10], autoimmune disorders, malignancy, or autonomic dysfunction)
11. > 6 one hour classes of meditation or other mind-body disciplines (e.g., Tai chi or yoga) within the last 6 months
12. Current individual or group psychotherapy established for <3 months
13. A subject who in the opinion of the Principal Investigator would not be able to safely complete the study or would jeopardize study integrity

14. History of heat intolerance or heat stroke
15. Unsafe cardiac status as defined by abnormal ECG reading at screening visit as determined by medical monitor, study doctor, or subject's PCP or cardiologist

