2. ECG												
3. Urine drug screen												
4. Urine pregnancy test (Female)												
Medical History	X											
Physical Examination by DCRP psychiatrist	X					X				X	X	
Habits Questionnaire	X					X				X	X	
MINI	X											
C-SSRS (lifetime and past year V1; since last visit all other visits)	X				X	X				X	X	X
Reproductive Status Questionnaire (Female)	X											
IDS-CR	X	X	X	X	X	X	X	X	X	X	X	X
HAM-D-28		X				X	X				X	X
Self-Rated Questionnaires: STAI; SF-36; Q-LES-Q; EIFI; PSS; PSQI; FFMQ; RRS	X	X	X	X	X	X	X	X	X	X	X	X
URICA		X				X	X				X	
Concomitant Medications	X	X	X	X	X	X	X	X	X	X	X	X
Vital Signs by research coordinator	X	X	X ⁺	X ⁺	X	X	X	X ⁺	X ⁺	X	X	X
Randomization		After baseline visit										
Psychoeducational Session		X					X					

Waist-to-Hip Ratio measured by research coordinator		X			X	X	X			X	X	X
Physiological Markers 1. Inflammatory markers (blood) 2. Cortisol (salivary)*		X			X	X	X**			X	X	X
Sleep Diary		X			X	X	X			X	X	X
Adverse Events		X	X	X	X	X	X	X	X	X	X	X
Hot Yoga Beliefs Scale		X				X	X				X	X
Acceptability Interview											X	
MINI Mood Module						X					X	X
QIDS-C and Weekly Phone Monitoring Form	<hr/> > On weeks in between V2-V3, V3-V4, V4-V5, V5-V6, V6-V7, V7-V8, V8-V9, V9-V10, V10-V11, V11-V12											
Pre- and Post-Yoga Scales over the STAI State, EIFI)	30 minutes prior to and 30 minutes post each yoga class											

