6.2.1 Screening Evaluation

Consenting Procedure

Prior to engaging in any study related activities, informed consent will be obtained by an MD- or PhD-level clinician or supervised psychology intern at the DCRP. One informed consent will be obtained for the screening and study procedures. Patients will be informed during the consent process that their participation is voluntary and their relationship with their prescribing physician will be unaffected by any choice to discontinue study participation. All participants will be informed that they can decline to answer any questions that they find upsetting and may withdraw from study participation at any time. The consent form will include the study procedures, information about potential risks and benefits of participation, and information regarding who they can contact with further questions or concerns. Patients will be alerted to the nature of the hyperthermic yoga practice during the consent process. Participants will have 24-hour pager access to an internal medicine physician, [name], whose specialty is in alternative medicine. This information will be given in the consent form. Documentation of informed consent will be kept in the Documentation of the Informed Consent Process for Onsite Subject File.

Visit 1: Screen – IYG and DYG

The screening visit will last approximately 3 hours. The purpose of this visit is to determine study eligibility. The two Figures above (6.1.1 and 6.1.2) outline the procedures for the screening visit, which are the same for the IYG and DYG. All of the screening items will be completed prior to the baseline visit (within 21 days of the screening visit).

- Informed Consent Form
- Demographics/Contact Information
- Clinician-Administered Psychiatric History Form
- Inclusion/Exclusion Criteria
- Safety Labs (i.e., blood, ECG, urine drug screen, urine pregnancy test [female] collected by a trained research coordinator)
 - Blood draw: A phlebotomy trained research coordinator at the DCRP will draw 11mL of blood (one 8mL tiger top tube and one 3mL lavender top tube).
- Medical History
- Physical Examination conducted by DCRP psychiatrist
- Habits Questionnaire
- MINI
- C-SSRS Lifetime and Past Year
- Reproductive Status Questionnaire (female)
- IDS-CR
- Self-Rated Questionnaires: STAI, SF-36, Q-LES-Q, EIFI, PSS, PSQI, FFMQ, RRS
- Concomitant Medications

- Vital signs
- Give salivettes and instructions to bring back salivary cortisol samples to their baseline visit

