6.2.2 Enrollment, Baseline, and/or Randomization

Enrollment

Enrollment is defined as the date all of the screening criteria are met— occurring between screening (visit 1) and baseline (visit 2).

Baseline Assessments (Visit 2 for IYG; Visits 2 and 7 for DYG)

At this visit subjects will meet with a study clinician for a 50-minute psychoeducational (see First Heated Yoga Class: What to Expect) and motivational session. Subjects will be asked to discuss reasons for wanting to try the hyperthermic yoga and also to discuss potential barriers to participation.

Visit 2: Baseline - IYG and DYG

- IDS-CR
- HAM-D-28
- Self-Rated Questionnaires: STAI, SF-36, Q-LES-Q, EIFI, PSS, PSQI, FFMQ, RRS, URICA
- Concomitant Medications
- Vital Signs
- Psychoeducational Session
- Waist-to-Hip Ratio
- Physiological Markers (i.e., inflammatory markers [blood], cortisol [saliva])
 - Please see section 9.5.2 for details
- Collect Sleep Diary (can bring to the following visit as long as it was completed for the right week)
- Collect salivates (can bring to the following visit as long as it was collected at the right time period)
- Adverse Events
- Hot Yoga Beliefs Scale

Visit 7: Repeat Baseline - DYG

- IDS-CR
- HAM-D-28
- Self-Rated Questionnaires: STAI, SF-36, Q-LES-Q, EIFI, PSS, PSQI, FFMQ, RRS, URICA
- Concomitant Medications
- Vital Signs
- Psychoeducational Session (refresher)
- Waist-to-Hip Ratio
- Physiological Markers[^] (i.e., inflammatory markers [blood], cortisol [saliva])
- Collect Sleep Diary (can bring to the following visit as long as it was completed for the right week)
- Adverse Events

- Hot Yoga Beliefs Scale

[^]If this visit takes place within 14 days of Visit 6, Physiological Markers will not be repeated at this visit.

At the end of the Baseline Visit that occurs before they start the yoga (V2 or V7), participants will be handed a packet of self-rated questionnaires (i.e. STAI-State and EIFI) to complete within 30 minutes prior and 30 minutes post each yoga class they attend. We will ask participants to note time and date on the top of each form. These questionnaires will provide data on acute mood changes pre- and post-yoga. [name] co-mentor [name] uses these questionnaires to gather the same data in her RO1 (5R01AT007483-05). Including this will allow us to compare data across studies.

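### Pregnancy status is checked only at screening, so the delayed group starts heated yoga about 12 weeks after its only scheduled check, against about 3 weeks in the immediate group

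*Combined protocol and SAP*

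**What the plan says.** Item 1 of section 4.2 excludes "Pregnancy or planned pregnancy during study", and inclusion criterion 7 requires birth control for women of childbearing potential.

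Two instruments bear directly on pregnancy status: the urine pregnancy test, which is one of the safety labs, and the Reproductive Status Questionnaire. Both schedules (6.1.1 and 6.1.2) mark the safety labs and the questionnaire at V1 only. The visit lists agree: both items are in the V1 list (6.2.1), and neither is in the lists for V2 and V7 (6.2.2), for V3 to V5 and V8 to V10 (6.2.4), or for V6, V11 and the one-month follow-up (6.2.5).

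Section 6.2.2 has an entry headed "Visit 7: Repeat Baseline - DYG" and identifies V2 (IYG) or V7 (DYG) as the baseline visit that precedes yoga. V7 repeats the depression ratings, self-ratings, concomitant medications, vital signs, waist-to-hip ratio and the psychoeducational session. Its distance from V6 is not fixed. The only reference is a footnote: "If this visit takes place within 14 days of Visit 6, Physiological Markers will not be repeated at this visit".

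Section 3 says that "the control or delayed yoga group (DYG) will complete the protocol in approximately 24 weeks" and gives about 15 weeks for the IYG.

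**The concern.** The sponsor already treats pregnancy status as relevant to taking part: it is an exclusion, contraception is required, and a test is done at entry. In the IYG that test comes shortly before the heated classes. In the DYG the whole waitlist period lies between the test and the first class, so a negative V1 result says much less about status when exposure begins. V7 is the natural place to look again, and it repeats other baseline items but not this one.

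What is at stake is the safety of women in the DYG's yoga phase. The intervention is at least two 90-minute classes a week for 8 weeks at 105–110°F. The protocol itself cites data that this yoga raises core body temperature (2.2), names fainting and heat stroke among the risks, and warns that instructors may urge participants to remain in the room (5.1).

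**Working it through.** **Inputs**
- Screening to baseline: at most 21 days, or 3 weeks (6.2.1)
- Waitlist, baseline to V6: 8 weeks (6.2.5)
- Yoga phase: 8 weeks (5.1); section 6.2.5 labels the DYG's V11 as week 9 of yoga
- Follow-up: 1 month, taken as 4 weeks (5.1)
- Totals: about 15 weeks IYG and 24 weeks DYG (section 3)
- Minimum classes: 16 (5.4), of 1.5 hours each

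**1. Reproduce the stated totals**
- IYG: 3 + 8 + 4 = 15 weeks.
- DYG: 3 + 8 + 1 (V6 to V7) + 8 + 4 = 24 weeks, or 3 + 8 + 9 + 4 = 24 using the 9-week label.

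The totals fit the visit structure, so they can be used to work backwards.

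**2. Only scheduled check to first class** (total − yoga − follow-up)
- IYG: 15 − 8 − 4 = 3 weeks.
- DYG: 24 − 8 − 4 = 12 weeks, or 24 − 9 − 4 = 11 with a 9-week yoga phase.
- Difference: 12 − 3 = 9 weeks (11 − 3 = 8).
- With a month of 4.33 weeks, the three intervals become about 2.7, 11.7 and 10.7.

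**3. Range, adding forwards** (screening gap + waitlist + V6-to-V7 gap)

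| Screening gap (weeks) | IYG | DYG, V7 0 / 1 / 2 weeks after V6 |
|---|---|---|
| 0 | 0 | 8 / 9 / 10 |
| 1 | 1 | 9 / 10 / 11 |
| 2 | 2 | 10 / 11 / 12 |
| 3 | 3 | 11 / 12 / 13 |

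The DYG range is 8 to 13 weeks and the IYG range 0 to 3. For any given screening gap the difference is 8 to 10 weeks. The footnote on physiological markers allows V7 to fall more than 14 days after V6 and sets no maximum. A 4-week gap would give 3 + 8 + 4 = 15 weeks, but also a total of 3 + 8 + 4 + 8 + 4 = 27 weeks, above the stated 24.

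**4. Exposure after the first class**

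Minimum class time is 16 × 1.5 = 24 hours.

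**5. Last class, measured from the latest scheduled check**
- IYG: 15 − 4 = about 11 weeks.
- DYG now: 24 − 4 = about 20 weeks.
- DYG with a test at V7: about 8 to 9 weeks.

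**6. What cannot be computed**

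The documents give no sex split, share of women of childbearing potential or contraceptive failure rate, so no expected number of pregnancies is offered.

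**The case against.** The strongest reply is that these women are seen and questioned repeatedly before their first class. At V6 the DYG has a physical examination and the Habits Questionnaire. Concomitant medications and adverse events are reviewed throughout the wait, bi-weekly calls run from baseline, V7 includes a clinician-led session, and section 8 allows withdrawal when a new physical condition comes to light. The consent form, phone monitoring form, Habits Questionnaire and preparatory handout are not shown, and any of them may ask about pregnancy or tell participants to report it. These are real mitigations, and they limit what can be said about the practical risk. None is specified as a pregnancy check, however. The events that section 7.3 solicits on the calls are depression, suicidality, muscle soreness and AEs/SAEs, and sections 7.1 and 8 act only once something has been found.

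A second reply is that 12 weeks is towards the top of the range, since it assumes the full screening window. That is fair, and 8 to 13 weeks is the better description. The gap between arms does not depend on that window.

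A third is that the IYG also goes about 11 weeks from its check to its last class, so the standard looks uneven, and that the documents set no retest interval. This stands as far as testing during the yoga weeks is concerned. The point here is narrower: whether there is a recent check before exposure starts. A V7 test would give the DYG a slightly closer check than the IYG has, since the IYG relies on V1 and is not retested at V2.

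Finally, section 5.1 names no pregnancy-specific hazard, and pregnancy is listed apart from the medical conditions said to make participation unsafe. The argument therefore rests on the sponsor's own exclusion and its stated heat risks, not on an estimated harm.

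**Conclusion.** The concern holds. Tables and visit lists agree that both pregnancy instruments are scheduled once, at V1, and that the DYG's pre-yoga visit repeats neither. On the protocol's nominal durations the DYG starts heated yoga about 12 weeks after its only scheduled check and the IYG about 3. Plausible ranges are 8 to 13 and 0 to 3 weeks, assuming V7 falls within 2 weeks of V6. The dates are approximate because neither the first class nor V7 is fixed.

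The finding concerns scheduled checks; unscheduled testing, or a question on a form not shown, cannot be ruled out. It is a safety gap confined to the DYG's yoga phase. Section 9.3 restricts the primary analyses to pre-crossover data, so the efficacy comparison, its power and its error rate are unaffected. The change should be made because it is cheap and makes the sponsor's own exclusion effective at the point of exposure.

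**What to change.** In table 6.1.2 and the Visit 7 list in 6.2.2, add the urine pregnancy test and the Reproductive Status Questionnaire for women, to be completed before the first yoga class. Add one sentence: a participant who tests positive does not start yoga, and her pre-crossover data stay in the primary analysis. The second half already follows from 9.3, but stating it avoids doubt.

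The cost is one test strip and one short form per DYG woman reaching V7. That is at most 40, and about 40 × 0.75 = 30 participants of both sexes reach that stage at the planned retention. Both instruments are already in use. V7 already takes vital signs and waist-to-hip ratio, and it is not one of the visits (3, 4, 8 and 9) at which vital signs may be omitted because the visit is by phone. If the V7 psychoeducation is done by phone, the test still has to be done before the first class.

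The one downside is possibly a few fewer crossover participants in the exploratory analyses. The change adds no testing during the yoga weeks in either arm.
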